METHODOLOGICAL PROCEDURES & DOCUMENTS MANUAL

Reducing Maternal Depression and Promoting Infant
Social-Emotional Health & Development

NIH R01 HD086894

NCT03464630

Randomized Controlled Trial Design: Prior to iPhone set up, the Intervention Project Coordinator implements randomization procedures. Using a random number generator, mother-infant dyads were randomized, in a 1:1 allocation, to one of the two parallel interventions: Mom and Baby Net or Depression and Developmental Awareness. The Intervention Project Coordinator notifies the PI to review condition assignment and assigns case to intervention coach. (see pages 26 and 98 in Procedures below)

Objective and Specific Aims:

The objective of this project was to address the problem of silo interventions and to improve accessibility to intervention that both reduces maternal depression and improves infant social emotional and communication development. To achieve this objective the following specific aims were addressed:

1. Embed core components of the Mom-Net Internet intervention into the Internet based virtual coaching intervention, Baby Net, to create Mom and Baby Net, an instructionally sound program geared to reduce the internal demands of depressed mothers postpartum.
2. Evaluate the impact of the Mom and Baby Net (MBN) program, as compared to a parallel Internet remote coaching intervention: Depression and Developmental Awareness (DDAS), via a randomized controlled trial. Depressed mothers during the postpartum period and their infants (N=180 dyads) will be randomized to the MBN or DDAS . Impact will be examined relative to:
 - 2.1 Change in parenting behavior, attitudes, beliefs, knowledge, and stress;
 - 2.2 Infant social-emotional behavior and development change;
 - 2.3 maternal depressive symptoms change; and
 - 2.4 Concomitant change in parenting, infant social-emotional, and maternal depressive symptom outcomes as a result of intervention.
3. Evaluate moderating influences on parent and infant behavior within the context of depression during the post partum period. We will focus on:
 - 3.1 The extent to which maternal depression prior to intervention, including current depression symptoms as well as depressive history and chronicity, relate to dosage within the MBN program;
 - 3.2 How dosage moderates parent and infant behavioral change as well as maternal depressive symptom change; and
 - 3.3 The extent to which contextual risks surrounding mothers (maternal isolation, social support and relationship status and conflict) not only relate to maternal depressive symptoms and MBN program dosage/skill acquisition but also moderate parenting, infant, and maternal depressive symptom change.
4. Assess maintenance of the program effects at 1-, 3- and 6-months after intervention. These trajectories for mothers and infants will allow for building a preliminary view of intervention effects as infants move into the next stage of development to determine if intervention early in infancy produces continued positive effects as these infants age.

PROCEDURES & DOCUMENTS TABLE OF CONTENTS

I. Recruitment and Screening.....	page 4
Procedures.....	page 5
Screening Script.....	page 7
Screening Documents.....	page 16
Recruitment Form	
II. Assessment Manual.....	page 17
Consent & Assessment Visit Procedures.....	page 18
Review and Sign Consent.....	page 20
Randomize Participant to Condition.....	page 26
Assessment Visit Documents.....	page 27
Consent Form	
Assessment Summary & Risk Identification	
Assessment Data Checklist iPhone	
Customization Questionnaire	
Resource Materials.....	page 38
Postpartum Depression Facts	
Crisis Help Card	
III. Coach Manual.....	page 68
Training Visit Procedures.....	page 69
Training Visit Documents.....	page 74
iPhone Agreement	
Coach Call Guidelines.....	page 76
Lost Contact Letter.....	page 78
IV. Safety Monitoring Documents.....	page 79
V. Adverse Event Guidelines.....	page 81
Decision Tree	
VI. COVID Remote Procedures*	page 84
Remote Recruitment and Screening Procedures.....	page 85
Remote Assessment and Training Procedures.....	page 95
Randomize Participant to Condition.....	page 98

I. Recruitment and Screening

RECRUITMENT & SCREENING PROCEDURES

RECRUITMENT PROCEDURES

Referrals from sites

Referral sites will be given referral materials to distribute to eligible participants. Eligible participants are mothers of babies age 0 – 12 months who live in the metro-Atlanta area, speak English, and meet criteria of depression on approved depression screening. Some sites will refer moms without screening for depression based on mom's age, location, and baby's age eligibility criteria. They will use the parent letter specific to sites that are not screening for depression.

Referral site home visitors will review the parent letter with eligible participants to tell them about the study and give them an interest card and envelope. The participant will complete the card, marking their interest and contact information, place in envelope, and return to their home visitor. The home visitor will write their initials on the outside of the envelope as well as the participant's score on the depression screening (number only) and baby's age. Home visitors will return envelopes to their site supervisor. The assessment coordinator will collect envelopes regularly in a manner agreed upon between the site and recruitment coordinator.

Some sites will also place a locked interest box in their office. The box will have information from the parent letter displayed with interest cards available for moms to read, complete, and place in the locked box. Research staff will check the boxes once a week and collect interest cards.

The assessment coordinator will open envelopes at GSU office. She will immediately shred any interest cards that are marked “not interested” and record the number of “not interested” cards and date collected in the Access database. She will assign an ID number to all “interested” cards and transfer contact information into the Access database.

The assessment coordinator will then contact interested participants and use the screening procedures to determine participants' full eligibility.

Referrals from community events

Research staff will attend community events that they are invited to attend or that they register to attend. As moms approach the project table, research staff will give them a parent letter (see Referral Site Packet) and read it with them. This letter tells them about the project and the eligibility criteria. If mom is interested in hearing more about the project, research staff will give them an ipad to complete the online screening and interest form.. Research staff will look at the screening form to confirm eligibility. If mom is not eligible, research staff will follow script on instructions sheet. If mom is eligible, research staff will tell her that they will call her to tell her more about the study.

Research staff will offer moms who are not eligible for the study a list of local resources (see 'Georgia Resources' section of the Mom & Baby Net handbook) and encourage them to reach out to the project team if needed (contact info on parent letter).

Online Referrals/Interest

Partners may direct eligible moms to the Mom & Baby Net website or moms may come to the website themselves. The website gives information about the program (same information as the parent letter) and includes an online screening and interest form. Moms will first answer 3 eligibility questions (mom age, baby age, and PHQ2 questions). If mom is not eligible based on this info, the form is completed and does not ask mom for contact information. For moms who are eligible, they will continue with the form and complete contact information.

The project coordinator will be notified by email when a form is submitted, go into Qualtrics, retrieve the information to a Recruitment Form, then delete the record from Qualtrics. The project coordinator will then continue with screening procedures below.

SCREENING PROCEDURES

Assessment coordinator will call interested participants. Prior to calling, assessment coordinator should have the participant's interest card, a blank recruitment form (see Recruitment Form) and the RCT consent form handy.

The assessment coordinator will then follow the Screening Call script and procedures to complete the screening call (see Screening Call Script). For referrals coming from sites that have not screened participant for depression, the screening call will include the depression screening as noted in Screening Call Script instructions.

MOM & BABY NET RCT RECRUITMENT CALL

After recording participant's responses to questions on the recruitment form, transfer the information to the Access Database & Matriculation Table

1. **Before the Call**
2. **Project Overview**
3. **Determine Eligibility**
4. **If Participant is Ineligible**
5. **Participant is Eligible**
6. **After the Call**

<><>

1. **BEFORE THE CALL**

- Have mom's interest card available.
- Have recruitment form ready to record mom's responses.
- Have RCT consent form ready to go over.

2. **PROJECT OVERVIEW**

Introduction: *Hello.....my name is _____ and I am calling from Georgia State University about a new research project called Mom & Baby Net.*

You recently said you'd like to hear more about the program to see if you could be included.

Thank you for your interest! I would like to tell you a little more about the project and see if you would be interested in participating and ask you a few questions to see if you are eligible. It will take about 15 – 20 minutes. You can stop the call at any time or tell me if you do not want to answer any questions. Is now a good time?

- If they can't talk now, set up a date and time for you to call again

About the project: *I have a couple of points I'd like to quickly share with you about the Mom & Baby Net project....if you have any questions, feel free to stop me at any time*

- *The purpose of this research project is to test two iPhone-based program for moms who have been feeling down and their babies. We hope to use this information to improve our program in order to help more moms.*
- *Participants in our study will be given an iPhone to access the program during the course of the study. There is no cost to your family for the loan of the iPhone for free data, texting, and phone calls to use while you are participating in the study. Upon completion of the program and assessment visits, participants will be able to keep the iPhone.*
- *Participating in this project will not affect any other services you currently receive.*
- *We have two different programs that provide information to mothers.*

- Both of the programs include 14 sessions with one session to be covered each week. Most moms spend between 40-60 minutes each week using the iPhone to work on the program and you can start and stop as needed. It will save your place. Each mom will be assigned an individual coach who will provide support through a video call each week. The call will involve watching a video that was created during the session. Each call will last about 20-30 minutes.
- Participants will be asked to complete 2 in-home assessments: 1 assessment visit at the beginning of the project and 1 assessment visit at the end. Each assessment visit will last about 1 to 1 ½ hours. If needed, we can split those into multiple visits. At each assessment visit we will make a video of you and your baby playing together and looking at books. We will also complete an online questionnaire that asks questions about you and your baby.
- Once you complete the first assessment, we will schedule one more home visit to give you the iPhone and support you in using it. This visit will last about 1 hour.
- There may be some benefits to mothers who participate in the program.
 - You may find that answering questions about parenting your baby is helpful and interesting.
 - You will have the iPhone with free data, texting, and calls to use during the study.
 - You will be able to keep the iPhone upon completion of the study. Although we will not continue to pay for phone service, you can use the phone through wireless Internet if you have access to it.
 - You will have the videos on the iPhone that you created during on the program.
 - You will be helping researchers to learn whether the program you receive is helpful for mothers of infants.
- There are few risks to being in the program.
 - You may feel uncomfortable answering some of the questions asked today or during the project. You can stop this call at any time and skip any questions during the project that you do not want to answer.
 - All information we collect is stored in a secure, locked office or database that is only accessible by approved research staff. We will use a study number rather than your name on all study records. There is only one code sheet use to identify research participants and it is stored securely in a password-protected file on a locked computer in a locked office.
- If you have any concerns or complaints, you can find IRB contact information at gsu.edu/irb

Does this sound like something you might be interested in hearing more about?

- If no: select DECLINE for final status and Eligibility Status; in the reason box next to Eligibility Status, select TOO BUSY/TIME or NOT INTERESTED
 - Do you have any other questions I could answer for you?
 - Thank you for your time. If you change your mind, feel free to contact me in the future to see if we are still recruiting.
- If yes, continue

3. DETERMINE ELIGIBILITY

Now we need to make sure that you are eligible for the project. There are some requirements for participating. Before spending any more time explaining the program, I would like to ask you a few questions to find out if you can indeed participate in this study. Are you comfortable with that? Your answers will be kept strictly confidential.

Age:

- *Are you 18 years of age or older?*
 - If Yes, continue and record mom's birth date on the recruitment form.
 - If No, **ineligible**. Go to page 5.

Residency

- *Do you live in the metro Atlanta area and plan to stay here during the next year?*
 - If Yes, continue
 - If No, **ineligible**. Go to page 5.

Baby

- *How old is your baby?*
 - Ask mom baby's age and date of birth. Record on recruitment form.
 - If baby is younger than 12 months, continue.
 - If baby is older than 12 months, **ineligible**. Go to page 5.

Stressful Situations

Sometimes families are experiencing stressful situations in their lives that can make it hard for them to be a part of a study such as this, either because the situation makes it burdensome for the family to participate in the study and/or because the family may need help that cannot be provided within the study. I am going to read you a list of some situations that families experience that make it a good idea for them to NOT participate in this study for the reasons that I just mentioned. You don't have to tell me which of these situations apply to you if any do. When I finish reading the list, I'll ask if any of these situations describe you.

- 1) *You have been diagnosed with schizophrenia.*
- 2) *You have received treatment or medication to help with hallucinations or delusions such as seeing or hearing things other people can't see or hear or having ideas that others might think are odd or strange, like people are out to get you or trying to hurt you.*
- 3) *You are currently receiving inpatient substance abuse treatment.*
- 4) *You live in a homeless shelter or domestic violence shelter.*
- 5) *Your infant is currently in intensive treatment for a genetic or health condition.*
- 6) *You do not have permanent legal guardian custody of your infant.*

Again, you don't have to tell me which of those might apply to you. However, please think about the situations I just mentioned, and answer "yes" or "no." Do any of these situations apply to you?

- If YES, **ineligible**. Go to page 5.
- If NO, continue.

Depression Screening (only do if not already completed by referring provider; mark responses on PHQ2 form)

Lastly, since our program is for moms who have been bothered by feeling down, we want to see how you've been feeling over the past 2 weeks. I'm going to read 2 statements with some answer choices for each one.

Over the past 2 weeks, how often have you had little interest or pleasure in doing things? Not at all, several days, more than half the days, or nearly every day?

Over the past 2 weeks, how often have you felt down, depressed or hopeless? Not at all, several days, more than half the days, or nearly every day?

- If score is less than 3, **ineligible**. Go to page 5.
- If score is 3 or higher, continue.

❖ **If participant is Eligible go to page 6**

4. IF PARTICIPANT IS INELIGIBLE

Thank the Mom for her time and let her know that she is not eligible (choose the response below that best fits with why the participant is ineligible).

Thank you for taking the time to answer my questions. Unfortunately you are not eligible for the project at this time.

- **Age:** *The project requires that moms be at least 18 years of age*
- **Baby:** *The project requires that babies be younger than 12 months of age at the time we begin the first assessment.*
- **Residency:** *The project requires that moms must live in the metro Atlanta area and remain there for the next year.*
- **Stressful situations:** *We have found that participation in the study is very challenging for those that are dealing with other stressful situations in their life.*
- **Depression screening:** *Based on our brief screening, there are no signs that you are struggling with depression symptoms at this time. But we know these feelings can change. If anything changes we encourage you to follow up with your doctor and or local community program or reach back out to us in a few weeks.*

Update contact and eligibility information in Matriculation Table.

File recruitment form in ‘Not Enrolled’ folder (program coordinator’s office).

5. **PARTICIPANT IS ELIGIBLE**

Based on the information you just gave me, you are eligible to participate in the program at this time. Before finalizing eligibility, we will confirm at our first visit that there is Sprint wireless coverage at your home. If you are interested in participating, the first step will be for us to come to your home to complete the first assessment. During that visit we will also go over the consent form, which will explain all the project details again. It will review exactly what you are being asked to do as well as the risks and benefits of being in this research study. We can answer any questions you have then before continuing.

What questions do you have right now? Answer any questions.

Schedule assessment visit: *I'd like to go ahead and set up a time to come visit for the first assessment. It's possible to finish all of the assessment in one visit, but that really depends on how long it takes for you to complete the questionnaire. We found it's best to block up to 2 hours of time for the visit. Then, we can just play it by ear. If you're not finished after an hour or so, we can schedule a second visit to finish up. Or, if you want to just power through and finish it in one visit, that's your choice as well.*

- *It's important to remember that the assessment visits are VERY different than the intervention. It's about gathering information about you and your baby – as compared to the intervention where you are going through an iPhone app on your own while learning information and watching fun videos of other moms and babies.*
- *When scheduling the 1st visit, it would be best to schedule this visit at a time of day when your baby is usually awake and alert since we will record you and your baby playing together.*
- *When is good for you? Is there a day or time that works best for you? Do you prefer mornings or afternoon?*
 - Record the scheduled appointment time in the Access Database along with any notes
 - Record appointment in the Mom & Baby Net Outlook calendar or other scheduling software

Confirm all the contact and demographic information and edit if necessary in the database:

- **NOTE:** Make sure to confirm if mailing address and physical address are different, confirm spelling of first and last name, and confirm date of birth and name of baby
- *Is this the best number to call to follow-up with you?*
- *Can we leave a message at this number? If it's a cell # - ask if you can text her appointment reminders.*
- *If for some reason I can't get a hold of you, it would be helpful to have some contact names and numbers of people who would be able to reach you. Do you have one or two people who typically stay in touch with you and know how to locate you even if you move or change numbers? Can I get their names and phone numbers?*
 - Record the contact names/numbers on the recruitment form

Recap:

- *I believe I have all the information I need. I'd like to quickly recap a couple of points*
 - *We will want your baby to be at the appointment so we can video tape you while you play and read together for about 10 minutes*
 - *We will need a quiet place for you and your baby to play together without interruptions*
 - *Again, we expect that the first visit will take approximately 1-1½ hours but we ask you to block off up to 2 hours. That way, if you want, you can finish everything in 1 visit and we won't need to schedule a 2nd assessment visit.*
 - *We have found that a lot of new moms worry about their house being messy or have concerns about having other people in their home. We are used to messy. We want you to be comfortable and we understand that with a new baby, there is a lot going on for you.*
- *Do you have any questions about the project in general?*
 - If yes, try and answer any questions they have or let them know you will call back with the answer.
 - If no, continue.
- *Give us a call if you have any questions or concerns before your scheduled appointment. We will also give you a reminder call or text the day before your appointment.*
- *We really want to thank you for your interest in our study and being willing to let us come to your home during this busy time in your life. We look forward to meeting with you on _____ at _____ am/pm.*

❖ **CONTINUE FOR 'AFTER THE INITIAL RECRUITMENT CALL' STEPS**

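### The single reply scripted for a PHQ2 total below 3 on the recruitment call is inaccurate for a mother who totals 1 or 2, because she has just reported low mood or loss of interest

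*Protocol*

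**What the plan says.** In Protocol section I, the depression screen is the last step under Determine Eligibility in the screening call script. The mother is asked "how often have you had little interest or pleasure in doing things" and "Over the past 2 weeks, how often have you felt down, depressed or hopeless". Each question has four ordered answers, from not at all to nearly every day. The exit rule is "If score is less than 3": she is then ineligible, and the caller turns to the ineligibility replies.

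Those replies are chosen by the reason for ineligibility, not by score. The depression reason has one reply: "Based on our brief screening, there are no signs that you are struggling with depression symptoms at this time". The script adds that such feelings may change, and continues: "If anything changes we encourage you to follow up with your doctor and or local community program". It also invites her to contact the study again in a few weeks. The remote recruitment call in section VI has the same rule and the same reply.

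Not every mother reaches this step:

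- The phone PHQ2 is marked "only do if not already completed by referring provider", and Screening Procedures says "For referrals coming from sites that have not screened participant for depression, the screening call will include the depression screening".
- For community events the instruction is "If mom is not eligible, research staff will follow script on instructions sheet", and that sheet is not among the documents.
- The web form closes by itself when a mother does not qualify.

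**The concern.** A total below 3 is not a total of zero. A mother can answer that she has felt down on some days, or even on most days, and still fall under the cutoff. She then hears that the screening found no signs of the problem she has just described, and the advice to see someone depends on a change from how she feels now.

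What is at stake is the accuracy of a health message to a mother of an infant at the point where she leaves the study. She came to the call after showing interest in a program for mothers who have been feeling low, so she may well take the reply as a finding about her health. The trial's data are not at stake.

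**Working it through.** The plan gives no figure to reproduce. The check has two parts: which answers lead to the reply, and how the reply compares with the study's handout.

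**Item scoring (assumption).** The PHQ2 form is not shown, so 0-to-3 scoring is inferred from two places that flag the same PHQ9 self-harm item:

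- Section II, on checking Qualtrics for safety concerns, flags the answers several days, more than half the days and nearly every day.
- Section VI, on recording embedded data on the ASRI, flags codes 1, 2 and 3.

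Matching the two lists gives several days = 1, more than half the days = 2 and nearly every day = 3, which leaves not at all = 0. The PHQ2 uses the same four answers.

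**Answers that lead to the reply.** With items ordered (interest, mood), there are 4 × 4 = 16 answer patterns. Those with a total below 3 are:

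| Total | Patterns | What she has reported |
|---|---|---|
| 0 | (0,0) | neither symptom |
| 1 | (0,1), (1,0) | one symptom on several days |
| 2 | (1,1) | both symptoms on several days |
| 2 | (0,2), (2,0) | one symptom on more than half the days |

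Only the (0,0) pattern fits a statement that there are no signs. Every pattern with a total of 1 or 2 includes a reported symptom. In (0,2), she has said that she felt down, depressed or hopeless on more than half the days of the past two weeks.

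**Sensitivity to the scoring.** If items were scored 1 to 4, the smallest total would be 1 + 1 = 2. The only total below 3 would then be not at all on both items, and the concern would vanish. The PHQ9 item coding above speaks against that scoring.

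**Reply and handout side by side.** The handout Postpartum Depression Facts, in the section II resource materials, lists sadness or hopelessness and loss of interest in usual pleasures among its symptoms. These closely match the two PHQ2 items. It advises a woman with any listed symptom to see a health care provider without delay. The call script gives a mother who has reported such a symptom that advice only if something changes.

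**The case against.** The strongest defence is that the sentence is plain language for a negative screen. It is limited by instrument (a brief screening), by degree (struggling) and by time (at present). The next words say that feelings can change, and three routes follow: her doctor, a community program, or the study again. The handout also describes baby blues as mild and short-lived, and a total of 1 or 2 may be no more than that.

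Part of this stands. The reply is qualified, it does not tell her to stay away from care, and nothing here shows that she has depression. But the qualifiers do not repair the central statement. The brief screening is exactly where she reported the symptom, and the remark about change concerns the future. The replies for mother's age, baby's age and residency state a project requirement, whereas this one makes a statement about her health. The handout itself leaves diagnosis to a health care provider.

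A reader might infer from the table that most screened-out mothers are misinformed, since five of the six patterns include a symptom. The documents do not support that. Patterns are not equally likely, and no score distribution is given. A reader might also infer that every ineligible mother hears this reply. That is not so: event and web failures leave by other routes, and provider-screened mothers skip the phone PHQ2.

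**Conclusion.** The point holds in a narrow form. For a mother given the PHQ2 on the call who totals 1 or 2, the scripted reply is inaccurate and sits badly with the study's own handout. This rests on 0-to-3 item scoring, which is inferred but well supported.

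The number of mothers affected cannot be derived from the documents. They are all outside the enrolled sample, so a reader should not infer any bias in the trial: eligibility, randomization, outcomes and analysis are untouched. This is a low-priority improvement that the team could make, worth doing because it is nearly free and gives a more accurate message to a mother who may be unwell.

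**What to change.** In the ineligibility replies of both the section I call script and the section VI remote script, replace the depression-screening reply with wording such as: *Your answers fall below the score this study uses. That does not mean you have no symptoms. If you are feeling down now, or start to later, please speak to your doctor.* Keep the existing invitation to contact the study again.

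The cost is a small text change in two scripts, with no extra staff, visits or data and no effect on the analysis. The Protocol's opening describes randomization in the past tense. If recruitment has closed, the change applies to any reuse of the script.
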